4. STUDY DESIGN

This is a prospective multicenter randomized controlled clinical trial. Endovascular treatment will be initiated on hospitalized patients who present with cerebral vasospasm within 3-21 days following surgical or endovascular intervention for aneurysmal subarachnoid hemorrhage (aSAH). Endovascular treatment will consist of:

- 1. Diagnostic angiogram to locate the spasmic blood vessel/vessels.
- 2. Pharmacological cerebral angioplasty to treat presenting spasm in one or two the following arterial vessel territories (if all three territories need treatment: the patient is excluded from participation in the study)
 - a. Right Carotid Artery Territory: to treat Vasospasm in R Carotid, R ACA, R MCA & its branches
 - b. Left Carotid Artery Territory: to treat Vasospasm in L Carotid, L ACA, L MCA & its branches
 - c. Vertebral-Basilar Territory
- 3. Post-treatment angiogram.
- 4. Balloon angioplasty may be done if vasodilators fail to produce response or show insufficient improvement.

Please refer to Appendix IV Study flow chart for the detailed study design & Flow

Randomization:

Study participants will be randomly assigned to one of three treatment groups. Randomization will be pre-determined and specific to each participating center. At each center only the Research Coordinator/Nurse will have access to the randomization pattern.

Treating physicians will not be blinded by the randomization scheme and will know the drug group assigned to the study subject *only after the first diagnostic angiogram has been performed, when he/she confirms the need for drug treatment.*

However, the subjects enrolled in the trial will be blinded and will not know the treatment group to which they have been assigned.

TREATMENT CRITERIA

- 1. Symptomatic vasospasm clinical symptoms, with or without Trans-cranial Doppler (TCD) study.
- 2. 50% or more stenosis seen on diagnostic angiogram in asymptomatic patients

DRUG DOSE: Patients who qualify for endovascular treatment post aSAH will be randomly assigned to one of three treatment groups:

Group 1: Nicardipine (Cardene): 5 mg per circulation in 25 mL 5% Dextrose. Infusion rate: 1.25 mL/minute over a period of 20 minutes

Group 2: Verapamil: 10 mg per circulation in 10 ml saline. Infusion rate: 1 mL/minute over a period of 10 minutes.

Group 3:

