Verapamil 10 mg in 10 mL saline, Infusion rate: 1 mL/minute over a period of 10 minutes + Nitroglycerin (200 mcg in 4 mL 5% dextrose, Infusion rate: 0.5 mL/min over 8 minutes + Nicardipine 5 mg in 25 mL 5% Dextrose, Infusion rate 1.25 mL/min over 20 minutes per circulation (USE DIFFERENT SYRINGES FOR EACH DRUG. DO NOT MIX DRUGS IN THE SAME SYRINGE.)

Perform post-treatment angiogram run minimally 10 minutes after completion of infusion. Angiographic Imaging should be recorded 10 minutes after infusion.

ONLY ONE TREATMENT SESSION is permitted per day.

Drug Dosage: Maximum intra-arterial dose allowed within 24-hour period is, nicardipine 10 mg, verapamil 20 mg, cocktail (verapamil 20 mg, nitroglycerin 400 mcg & nicardipine 10 mg)

Please refer to Appendix V & VI for detailed drug dosage tabulations.

If the study subject needs another treatment after the first treatment session, use the same drug for each repeat treatment.

Additional doses can be given per the treating physician's discretion up to the maximum allowed dose as per the protocol; please record the additional doses and treatment given in the data collection forms.

Balloon angioplasty can be performed if drug infusions show insufficient improvement per the treating physician's discretion.

A central core laboratory will perform radiographic data assessment and assessors will be blinded to treatment group assignment.

The diameters of the same spasm vessel(s) will be compared before (pre-) and after (post-) infusion of the agent/agents, (see figure below).

The diameters will be measured at the following locations: ICA supraclinoid segment, MCA M1, MCA M2, ACA A1, ACA A2 & Basilar

The pre-treatment diameter measurement will be at the narrowest spot as is shown in the figure below. The post-treatment diameter measurement will be at the same location as the one prior to the infusion treatment.

Pre-infusion

Post-infusion

The changes will be quantitated based on the ratio percentage as shown in the following formula.

Post-infusion improvement ratio (PIIR) = (B - A)/A

Example: A = 1 mmB = 1.2 mm

PIIR % = (1.2 - 1)/1 = 20%

If balloon angioplasty is performed, the artery diameter will still be measured and the measurement documented.

Clinical data, that will be collected and entered in REDCap are as follows:

- Patient demographics (age, gender, BMI, race)
- Patient medical and surgical history
- Patient's current medications

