10. STATISTICAL CONSIDERATIONS

Design:

The clinical trial will be conducted under a common umbrella protocol developed by the primary site (UTH) with the intention of combining data from all satellite centers for analysis. Each investigational site will give utmost importance to follow the study protocol to maintain consistency in study execution at all centers. Patients will be randomly assigned to 3 treatment groups in a 1:1:1 allocation ratio. The three therapeutic regimens to be considered are:

Group 1: nicardipine (Cardene) 5 mg per circulation in 25 mL of 5% Dextrose,

Group 2: verapamil 10 mg per circulation in 10 mL saline

Group 3: Cocktail agents: 5 mg in 25 mL 5% Dextrose + verapamil 10 mg in 10 mL saline + nitroglycerin 200 mcg in 4 cc of D5W per circulation.

A maximum of 330 subjects, 110 per treatment arm, will be randomized. The trial includes interim analyses that may reduce the maximal sample size if clear differences emerge among the arms during the conduct of the trial.

Interim Analyses:

Interim analyses will be performed to allow for discontinuing enrollment to treatment arms due to futility. After approximately 90 subjects have been randomized, 30 per arm, interim analyses will begin at the next quarterly Data and Safety Monitoring Board (DSMB) meeting. Subsequent interim analyses will be performed to coincide with DSMB meetings, which will occur after 40 subjects, 70 subjects, 110 subjects, 165 subjects, and 248 subjects have completed the study, and at the conclusion of the study (330 subjects).

At each interim analysis, an Analysis of Variance (ANOVA) will be performed to compare the PIIR results across treatment arms. If the overall treatment effect is significant with a p-value<0.05, then pairwise treatment comparisons will be performed. If any pairwise comparison is significant at a Tukey's adjusted two-sided p-value of 0.02 (p< 0.02), the poor performing arm will be dropped from the randomization scheme. If multiple arms are dropped and only one treatment arm remains open for randomization, that arm will be declared as best, and the clinical trial will end. Pairwise comparisons will only be performed if the overall treatment effect in the ANOVA is significant.

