A maximum of 110 subjects will be randomized to each treatment arm, for a total sample size of 330. If an arm or arms are dropped early, the final sample size will be less than 330. For example, suppose an interim analysis is performed after 70 subjects are randomized to the 3 treatment arms (total sample size 210). Suppose further, at the interim analysis one arm is dropped, and the remaining two arms continue to enroll to completion. The final sample size will be 290, i.e., 70 subjects in the dropped treatment arm, and 110 in each of the remaining treatment arms.

Enrollment will continue while the interim analyses are performed

Final Analyses:

All patients will be included in analyses utilizing the Intent-to-Treat approach that includes all subjects randomized in their randomized treatment arm regardless of treatment received.

At the final analysis, the primary outcome measure, PIIR will be compared between treatment arms using an ANOVA model. All data will be used in the final analysis, including any arms that may have been dropped from the randomization. If the overall treatment effect in the ANOVA model is significant at the two-sided, 5% level, then pairwise comparisons among treatment arms will be conducted using Tukey's adjusted p-values with p<0.0330 declared as statistically significant. This value controls global type I error (mistakenly claiming any pairwise difference when all treatments are equal) accounting for 6 interim analyses at the anticipated accrual rate of 2 years. If accrual significantly deviates from the anticipated accrual rate, further trial simulations will be conducted to determine an appropriate adjustment for the actual number of interim analyses conducted.

Descriptive statistics, means, medians, and standard deviations, will be reported for PIIR in each treatment arm. The two-sided 95% confidence interval will also be presented for the PIIR in each treatment arm.

The key secondary outcome, mRS (Modified Rankin Scale) at 3-months post-treatment, will be summarized by treatment arm by reporting the counts and proportions in each mRS category. Comparisons among treatment groups will be made using a Chi-square test.

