Additional secondary outcomes include SAE (severe adverse event) occurrences and the rate of treatment failure with balloon angioplasty. These outcomes will be summarized descriptively by presenting rates and proportions. Exploratory analyses comparing outcomes between treatment arms will be made using a Chi-square test.

Additional exploratory multivariable linear regression models will be created for the PIIR outcome, adjusting for treatment groups and additional baseline factors.

The analyses for the secondary outcomes are considered exploratory and no adjustments for the multiple tests and multiple comparisons will be made. Results will be interpreted cautiously understanding the some results may be significant at the 5% level due to chance alone.

Sample Size Justification:

Simulations were performed to estimate the power of the study for the primary outcome measure, PIIR, with a maximum sample size of 330 (110 per treatment arm) and the interim analyses for possible early arm dropping. A range of scenarios of PIIR were examined; the key scenarios used to power the trial are presented in Table 2.

Table 2.

Scenario	Treatment Arm 1: Nicardipine (N)	Treatment Arm 2: Verapamil (V)	Treatment Arm 3: Combination (C)
Combo 20	0.10	0.10	0.30
Mixed 1530	0.10	0.15	0.30

Note that the scenarios are both in favor of Verapamil over Nicardipine, but the results are symmetric if Nicardipine and Verapamil were reversed.

The trial will make every pairwise comparison:

- N versus V
- N versus C
- V versus C

The simulations focused on the V>N, C>N, and C>V comparisons. The following table presents the expected (mean) sample size and probability that the combination treatment regimen is better than the verapamil regimen, i.e., Pr(C>V), the main comparison of interest. Power is defined as the probability of identifying the superiority of the best dose over the other two doses.

Table 3.

Scenario	Expected N	Power Pr(C>V)
Combo 20	177	0.95
Mixed 1530	211	0.77

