Table 3 demonstrates, that for a hypothesized scenario of "Combo 20" where the combination therapy PIIR is 0.30 compared to 0.10 in Nicardipine and Verapamil, the study will have over 90% power and an expected sample size of 177. Both the Nicardipine and Verapamil arms would have been dropped at interim analyses before they reached their maximum enrollment of 110. If the scenario of "Mixed 1530" is observed, a situation where the Nicardipine arm PIIR is 0.10, the Verapamil arm PIIR is 0.15 and the combination arm is 0.30, the study will have 77% power and an expected sample size of 211. Again, both the Nicardipine and Verapamil arms would have been dropped at interim analyses before they reached their maximum enrollment of 110.

Missing Data and Dropout Rate: We do not anticipate missing data for the primary outcome PIIR as the angiogram will be performed 10 minutes post-infusion. For the secondary outcome, mRS at 3-months, based on previous studies, we estimate up to a 20% loss follow-up. Efforts will be made to keep all patients in the study through the 3-month follow-up visit. Substantial efforts will be made to ensure complete follow-up. Rates of missing data and loss to follow-up will be reported by treatment arm. We will attempt to document maximum amount of information regarding the status of these

patients who drop out. This procedure will help to compare characteristics of those patients who completed the study with those who did not.

Data and Safety Monitoring:

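### The interim and final tests of PIIR adjust for neither centre nor pre-infusion diameter: precision may be lost, and contrasts with a dropped arm may be biased

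*Combined protocol and SAP*

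**What the plan says.** Section 10 describes the interim test as follows: "At each interim analysis, an Analysis of Variance (ANOVA) will be performed to compare the PIIR results across treatment arms". The final test is worded in the same way: "At the final analysis, the primary outcome measure, PIIR will be compared between treatment arms using an ANOVA model". No covariate, stratum or centre term is named in either place. Adjustment appears only later in the same section: "Additional exploratory multivariable linear regression models will be created for the PIIR outcome, adjusting for treatment groups and additional baseline factors". Those baseline factors are not listed.

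Two candidate terms are already in the design. Section 4 (Randomization) says: "Randomization will be pre-determined and specific to each participating center". It does not say whether the centre lists are blocked. Section 4 also says: "The pre-treatment diameter measurement will be at the narrowest spot as is shown in the figure below". That diameter, A, is the denominator of the outcome: "Post-infusion improvement ratio (PIIR) = (B - A)/A". Six segments may be measured, so one patient can contribute more than one diameter.

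Section 10 drops the worse arm from randomisation at an interim, yet keeps its data in the final ANOVA. Its worked example ends with 70 patients in the dropped arm and 110 in each of the others.

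**The concern.** Centre is the only grouping that the randomisation names, and A is a baseline value that has to be measured to compute PIIR at all. If either predicts PIIR within arms, an arm-only ANOVA leaves that variation in its error term. The scenario with room to gain is Mixed 1530, where the plan states power of 0.77 for combination over verapamil, its main comparison.

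Arm dropping raises a second matter. Once an arm closes, the remaining arms go on recruiting, possibly from a different mix of centres. The final ANOVA then compares the closed arm with patients who could not have been assigned to it.

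**Working it through.** **Reproducing Table 3.** The plan gives power 0.95 (expected N 177) for Combo 20 and 0.77 (N 211) for Mixed 1530, but not the SD. The stated rule was simulated: overall F at p<0.05, Tukey p<0.02 to drop an arm, Tukey p<0.0330 at the end, cap 110 per arm. C>V counts if verapamil is dropped in favour of the combination or if the final test shows it. Looks were at 90 and then about quarterly.

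| SD | Combo 20 power (N) | Mixed 1530 power (N) |
|---|---|---|
| 0.35, common | 0.965 (184) | 0.778 (217) |
| 0.34, common | 0.972 (177) | 0.802 (211) |
| 0.12, 0.12, 0.366 (Section 3) | 1.00 (115) | 0.97 (144) |

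SD 0.35 comes close to both power figures but not to N for Combo 20 (184/177 = 1.04). It is a calibration, not a documented value.

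**Precision.** With correlation r between diameter and PIIR within arms, residual SD = SD × √(1 − r²). At r = 0.3 this is 0.35 × √0.91 = 0.334, equivalent to 1/0.91 = 1.10 times the patients.

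The models were then fitted in simulated trials (20,000 per cell). Assumptions: five centres with shares 0.40/0.20/0.15/0.15/0.10, blocks of 6 within centre or no blocks, SD 0.35, looks at 90/110/165/248. Section 10 also mentions looks at 40 and 70; looks at 40/70/110/165/248 gave results within 0.002.

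| Mixed 1530, Pr(C>V) | Blocked | Unblocked |
|---|---|---|
| Arm only | 0.775 | 0.774 |
| Adjusted, r = 0 | 0.774 | 0.764 |
| Adjusted, r = 0.1 | 0.778 | 0.769 |
| Adjusted, r = 0.2 | 0.791 | 0.783 |
| Adjusted, r = 0.3 | 0.815 | 0.808 |

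- If centre explains 10% of PIIR variance, power goes from 0.781 to 0.819 (blocked) or from 0.770 to 0.813 (unblocked).
- Combo 20, blocked: 0.963 arm only, 0.976 adjusted at r = 0.3.
- Section 3 SDs, Mixed 1530: 0.968 arm only; adjusted 0.967 at r = 0 and 0.977 at r = 0.3.

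**What r could be.** Because A is the denominator, the formula can itself induce a correlation. For an assumed coefficient of variation of A of 0.2 to 0.4 and measurement error of 0 to 10%, r is 0 to -0.17 if the absolute gain is proportional to A, and -0.06 to -0.38 if the gain does not depend on A. A gain that rises more than proportionally could offset this.

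**Bias after a drop.** Let a centre group's share of enrolment move from s₁ before the drop to s₂ after it, and let its mean PIIR differ by d. If an arm closes at n patients, the share in an arm that continues to 110 is [n·s₁ + (110 − n)·s₂]/110, and bias = d × (that share − s₁).

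- Close at 70 (the plan's example), 0.2 to 0.8, d = 0.20: share = (14 + 32)/110 = 0.418; bias = 0.20 × 0.218 = 0.044.
- Close at 70, 0.4 to 0.6, d = 0.05: share = (28 + 24)/110 = 0.473; bias = 0.05 × 0.073 = 0.004.
- Close at 30, the same two cases: 0.20 × (0.636 − 0.2) = 0.087 and 0.05 × (0.545 − 0.4) = 0.007.

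In simulation (SD 0.40, no true difference) the extreme drift with d = 0.20 gave a rejection rate at nominal 5% of about 18% (close at 30) or 10% (close at 70). With centre in the model it was 5 to 6% and the bias about 0. With no arm dropped, the bias was 0 even under drift. All drift values are assumptions.

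**Error rate.** At SD 0.35 with looks from 90, the null rate of a false final pairwise claim is 0.049 with either model. Counting false interim drops as well, it is about 0.07, again with either model. If lists are blocked and centre explains 10% of variance, the rate of a false final claim is 0.033 unadjusted and 0.049 adjusted; without blocking it is 0.048 and 0.049.

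**The case against.** An unadjusted primary test is legitimate, and the plan already intends adjusted regressions of PIIR, if only as exploratory work. No document supports a correlation of 0.3 or any centre effect. At r = 0.1 the change is +0.3 point (blocked) or -0.5 point (unblocked), and with no prognostic value and unblocked lists about 1 point is lost. The only SDs in the documents leave a gain of about 1 point. No single diameter per patient is defined, so the covariate needs a rule first. The linear model also keeps the pooled variance, although the retrospective SDs differ threefold (12.0 and 36.6).

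All of this stands. It makes the point an improvement to consider and rules out a firm promise of power. It does not reduce the point to taste: the terms are specific, one of them is the randomisation stratum, and both are already collected.

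That the ANOVA contains arm alone is an inference from silence. It is a fair one, because the plan places covariates in a separate exploratory model.

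**Conclusion.** The point holds as a modest efficiency matter with one qualification about bias. At SD 0.35, adjusting changes Mixed 1530 power by about 0 (blocked) to -1 point (unblocked) if neither term predicts PIIR, and by +3 to +4 points at r = 0.3 or if centre explains 10% of variance. Combo 20 gains about 1 point. SD, correlations, centre shares and blocking are all assumed.

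Three stronger readings are not supported:

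- A reader might infer that leaving out centre and diameter biases the primary comparison. Among concurrently randomised arms it does not.
- A reader might infer the opposite, that no bias can arise. That fails for a dropped arm if the centre mix or period effects change. Section 10 expects both single-agent arms to be dropped in its two scenarios, so the case is not remote. The documents do not say how much drift to expect, and the largest values above need extreme drift.
- A reader might take the 0.049 null rate as proof that the thresholds control error. It leaves out false interim drops. The figure of about 0.07 is no argument against adjustment either, since both models give it.

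**What to change.** Before any comparative data are seen:

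1. Make the primary interim and final model a linear model of PIIR on arm, centre (with a fixed rule for pooling very small centres) and one prespecified per-patient pre-infusion diameter. Take the overall arm test and the Tukey contrasts from it.
2. Use one per-patient rule for both PIIR and the diameter, since the plan lists several segments: "The diameters will be measured at the following locations: ICA supraclinoid segment, MCA M1, MCA M2, ACA A1, ACA A2 & Basilar". Centre the diameter on its segment mean pooled over arms, so that it does not merely encode the segment. With half of the diameter variance assumed to lie between segments and r = 0.3 within them, Mixed 1530 power was 0.815 with centring and 0.793 with the raw diameter.
3. Keep the arm-only ANOVA as a sensitivity analysis.
4. Add a sensitivity analysis restricted to concurrently randomised patients for every contrast with a dropped arm. A centre term deals with a changing centre mix but not with a period effect within centres.
5. Rerun the simulations with this model, stating the SD and correlations, to confirm 0.02 and 0.0330. Count false interim drops as well as final claims in the null rate.

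The cost is SAP text, the per-patient rule and a simulation rerun of a kind Section 10 already foresees. No new data are needed. The model uses at most 5 degrees of freedom: Section 5 lists four centres and Appendix I five, so up to four for centre and one for diameter. The price is up to about 1 point of power if neither term is prognostic.

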2. STUDY OBJECTIVES

Primary Objective: The primary objective of the study is to determine the optimal intra-arterial drug treatment regimen for arterial lumen restoration after cerebral vasospasm following aneurysmal subarachnoid hemorrhage.

We hypothesize that a cocktail of drug agents via infusion will likely improve treatment efficacy compared to single agents.

Secondary Objective: The secondary objective is to evaluate clinical outcome 90-days after patient discharge following in-hospital optimal intra-arterial drug treatment for cerebral vasospasm

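### Key secondary outcome (3-month mRS): chi-square on an unstated table, with no pre-specified between-arm estimate or confidence interval; a named ordinal model would be a cheap improvement

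*Combined protocol and SAP*

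**What the plan says.** All of this is in Section 10, Final Analyses, unless noted.

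- Status: mRS is singled out as "The key secondary outcome, mRS (Modified Rankin Scale) at 3-months post-treatment". Section 2 sets the matching aim: "The secondary objective is to evaluate clinical outcome 90-days after patient discharge".
- Description: mRS "will be summarized by treatment arm by reporting the counts and proportions in each mRS category".
- Comparison: "Comparisons among treatment groups will be made using a Chi-square test". No cut-point, table dimensions, global or pairwise use, ordinal or trend test, odds ratio, risk difference or between-arm CI for mRS appears anywhere.
- Standing: "The analyses for the secondary outcomes are considered exploratory and no adjustments for the multiple tests and multiple comparisons will be made".
- For PIIR, the primary outcome: "The two-sided 95% confidence interval will also be presented for the PIIR in each treatment arm". Also: "Additional exploratory multivariable linear regression models will be created for the PIIR outcome, adjusting for treatment groups and additional baseline factors". No model of any kind is planned for mRS.
- Baseline data: the list in Section 4 includes "Patient demographics (age, gender, BMI, race" and both mRS and NIHSS before treatment.

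**The concern.** The primary outcome is angiographic and is read 10 minutes after infusion. mRS is the outcome the plan names for judging whether patients fare better. It is an ordered scale. A Pearson chi-square on all its levels gives the same result if the levels are shuffled, so it spreads its sensitivity over every possible pattern, including ones nobody expects. If one regimen moves patients towards better function overall, a test that uses the order will detect this more often.

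A chi-square p-value also does not say which arm did better, by how much, or what the data can exclude. For an exploratory outcome in a trial powered on something else, the size of the difference and its precision are what a reader needs most. At stake is how informative the clinical result will be. The primary analysis and the arm-dropping rules are not affected.

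**Working it through.** The documents give no power, effect size or expected distribution for mRS, so there is no mRS figure to reproduce. The check asks what the stated test costs compared with one that uses the order.

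**Inputs from Section 10.** Three arms; at most 110 per arm; up to 20% lost to follow-up for mRS; expected N of 177 under the Combo 20 scenario.
- No arm dropped: 110 x 0.8 = 88 followed per arm.
- Expected N: 177 x 0.8 = 141.6, and 141.6 / 3 = 47 per arm if split equally.

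**Assumptions, not in the documents.** Single-agent mRS 0 to 6 distributed 10/15/15/15/15/10/20%. The combination arm is shifted by a common OR: at every cut, its cumulative odds equal OR times the single-agent odds. For mRS 0-2 the single-agent share is 0.40 (odds 0.667). At OR 1.8 the odds become 1.2 and the share 1.2 / 2.2 = 0.545.

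**Tests, two-sided 5%.** Seven-level chi-square, (3 - 1) x (7 - 1) = 12 df; Kruskal-Wallis (2 df) for the ordinal test; chi-square on 0-2 v 3-6 (2 df). There were 20,000 simulated trials per cell, except the OR 1.3 row, where two runs of different size give the ranges shown.

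| Scenario | 88 per arm: chi-square / ordinal | 47 per arm: chi-square / ordinal |
|---|---|---|
| OR 1.0 | 0.05 / 0.05 | 0.05 / 0.05 |
| OR 1.3 | 0.08-0.09 / 0.16 | 0.06-0.07 / 0.11 |
| OR 1.6 | 0.20 / 0.43 | 0.12 / 0.24 |
| OR 1.8 | 0.31 / 0.62 | 0.16 / 0.36 |
| OR 2.5 | 0.74 / 0.96 | 0.40 / 0.73 |

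The OR 1.0 row shows that both tests hold their level. At moderate shifts the chi-square has about half the power of the ordinal test; the relative loss shrinks as the effect grows.

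**How far this depends on the set-up.**
- Other distributions: three alternatives at OR 1.8 and 88 per arm give 0.31-0.32 v 0.62-0.63.
- Pairwise 2 x 7 tables (6 df), 88 v 88, OR 1.8: 0.32 v 0.60.
- Split at 0-2 v 3-6, 88 per arm: 0.34 at OR 1.6 and 0.51 at OR 1.8, about 80% of the ordinal power (0.34 / 0.43 = 0.79; 0.51 / 0.62 = 0.82).
- Unequal arms after dropping (32/32/78, assumed), OR 1.8: 0.19 v 0.40.
- Fitted proportional-odds likelihood-ratio test (1,500 trials), OR 1.8: 0.64 at 88 and 0.34 at 47 per arm, so Kruskal-Wallis is a fair stand-in.
- Not a shift, 88 per arm: 12 points moving from mRS 6 to 5 gives 0.57 for chi-square v 0.07 for the ordinal test; 12 points from mRS 3 to 2 gives 0.62 v 0.07.

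**What the CI would show.** 95% CI = exp(ln OR +/- 1.96 x SE), with ln 1.8 = 0.588.
- 88 per arm, mean SE 0.267: exp(0.588 +/- 0.523) = 1.1 to 3.0.
- 47 per arm, mean SE 0.368: exp(0.588 +/- 0.721) = 0.9 to 3.7.

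**Using both tests.** With no effect, the chance that at least one of the seven-level chi-square and the ordinal test gives p < 0.05 is about 0.09.

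**The case against.** The strongest reply is that little is at stake. The plan calls these analyses exploratory, leaves them unadjusted, asks for cautious reading and ties no decision to mRS. The stated objective is to evaluate clinical outcome, which the tabulated distribution by arm already does in part. The test is valid. That all stands, and it sets the weight of the point. It does not supply an estimate or a CI.

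The power argument is also conditional, and this stands too. Seven levels is an inference from the per-category summary that comes just before the test. A common-OR shift is the pattern that favours an ordinal test, and no document says which pattern to expect. The larger power figures need 88 followed per arm, whereas Section 10 expects both single-agent arms to be dropped early in both powering scenarios. Near the expected N, both tests are weak.

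Two stronger readings are tempting, and the documents do not support them. A reader might infer that the plan will report nothing for mRS but a p-value. In fact the full distribution by arm is pre-specified, and a crude difference can be derived from it; what is missing is a contrast and interval chosen in advance. A reader might also infer that PIIR gets the between-arm estimate that mRS is denied. The PIIR interval is within each arm, and the adjusted PIIR models are exploratory, so that contrast is thin.

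**Conclusion.** The point holds as a modest, cheap improvement. Two parts rest on the text alone: the table to be tested is not stated, and no between-arm mRS estimate or CI is pre-specified. The missing estimate matters on any reading of the test.

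The loss of power is conditional. It needs a seven-level table and an overall shift. On the assumed distributions it is about half at moderate effects, less if the scale is split at 0-2 v 3-6, and of little practical use at OR 1.3, where neither test helps. It turns into an advantage for chi-square when patients move between adjacent levels without an overall shift. A reader should not conclude that the chi-square test is wrong or always inferior.

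Section 10 counts the three months from treatment and Section 2 from discharge. That is a separate matter and carries no weight here.

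**What to change.** In Section 10, Final Analyses, replace the mRS comparison sentence with the following plan.

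1. One named comparison: a proportional-odds logistic regression of 3-month mRS on arm, with death scored 6, adjusted for age and one baseline score named in advance, for example pre-treatment NIHSS.
2. Report the common OR with 95% CI for each pair of arms.
3. Keep the category counts, and keep the chi-square test, stated to be on all seven levels, as supportive only. Fix these roles before the data are seen, because reading either test as positive raises the false-positive chance from 0.05 to about 0.09.
4. Keep the exploratory label.

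The cost is wording: the covariates are already collected, and no visit or patient is added. There are two downsides to state. The ordinal model has little power for patterns that are not a shift, which is why the counts and the chi-square stay alongside. If the odds are not proportional, the common OR is only an average and must be read with the counts.

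The gain from adjustment depends on how prognostic the covariate is. With an assumed conditional treatment OR of 1.8 and 88 per arm, power goes from 0.58 to 0.60 for a weaker covariate (OR 1.65 per SD), which is within the simulation error of about 0.025, and from 0.48 to 0.60 for a stronger one (OR 2.7 per SD).
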